#### 7.1.5 Management of Toxicity

See Appendix II for full details of toxicity management.

For adverse events (AEs) that are considered at least partly due to administration of nivolumab and/or ipilimumab the following dose adjustment guidance may be applied:

- Treat each of the toxicities with maximum supportive care (including holding the agents suspected of causing the toxicity where required).
- If the symptoms promptly resolve with supportive care, consideration should be given to continuing nivolumab or ipilimumab along with appropriate continuing supportive care. If medically appropriate, dose delays are permitted for nivolumab and/or ipilimumab (see Appendix II).
- All dose delays should be documented with clear reasoning and documentation of the approach taken.
- In addition, there are certain circumstances in which nivolumab or ipilimumab should be permanently discontinued.

#### 7.1.6 Management of Infusion Reaction

Since nivolumab and ipilimumab contain only human immunoglobulin protein sequences, they are unlikely to be immunogenic and induce infusion or hypersensitivity reactions. However, if such a reaction were to occur, it might manifest with fever, chills, rigors, headache, rash, urticaria, angioedema, pruritus, arthralgias, hypo- or hypertension, bronchospasm, or other symptoms.

All Grade 3 or 4 infusion reactions should be reported as an SAE if criteria are met. Infusion reactions should be graded according to NCI CTCAE version 5.0 guidelines

##### **For Grade 1 symptoms:**

(Mild reaction; infusion interruption not indicated; intervention not indicated)

Remain at bedside and monitor patient until recovery from symptoms. Infusion rate may be slowed. If the infusion is interrupted, then restart the infusion at 50% of the original infusion rate when symptoms resolve; if no further complications ensue after 30 minutes, the rate may be increased to 100% of the original infusion rate. Monitor patient closely.

The following prophylactic premedications are recommended for future infusions: diphenhydramine 50 mg (or equivalent) and/or paracetamol 325 to 1000 mg (acetaminophen) at least 30 minutes before additional nivolumab or ipilimumab administrations, slowing infusion rate as above.

##### **For Grade 2 symptoms:**

(Moderate reaction requires therapy or infusion interruption but responds promptly to symptomatic treatment [e.g. antihistamines, non-steroidal anti-inflammatory drugs, narcotics, corticosteroids, bronchodilators, IV fluids]; close observation for recurrence and treatment medications may need to be continued for 24-48 hours)

Stop the nivolumab or ipilimumab infusion, begin an IV infusion of normal saline, and treat the patient with diphenhydramine 50 mg IV (or equivalent) and/or paracetamol 325 to 1000 mg (acetaminophen); remain at bedside and monitor patient until resolution of symptoms. Corticosteroid or bronchodilator therapy may also be administered as appropriate. If the infusion is interrupted, then restart the infusion at 50% of the original infusion rate when symptoms resolve; if no further complications ensue after 30 minutes, the rate may be increased to 100% of the original infusion rate. Monitor patient closely. If symptoms recur, then no further nivolumab or ipilimumab will be administered at that visit. Administer diphenhydramine 50 mg IV, and remain at bedside and monitor the patient until resolution of symptoms. The amount of study drug infused must be recorded on the electronic case report form (eCRF).

The following prophylactic premedications are recommended for future infusions: diphenhydramine 50 mg (or equivalent) and acetaminophen (or paracetamol) 325 to 1000 mg should be administered at least 30 minutes before additional nivolumab administrations. If necessary, corticosteroids (recommended dose: up to 25 mg of IV hydrocortisone or equivalent) may be used.

**Grade 3 symptoms:**

(Severe reaction; prolonged [i.e. not rapidly responsive to symptomatic medication and/or brief interruption of infusion]; recurrence of symptoms following initial improvement; hospitalization indicated for other clinical sequelae [e.g. renal impairment, pulmonary infiltrates])

**Grade 4 symptoms:**

(life threatening; pressor or ventilatory support indicated)

Immediately discontinue infusion of nivolumab or ipilimumab. Begin an IV infusion of normal saline, and treat the patient as follows. Recommend bronchodilators, epinephrine 0.2 to 1 mg of a 1: 1,000 solutions for subcutaneous administration or 0.1 to 0.25 mg of a 1: 10,000 solution injected slowly for IV administration, and/or diphenhydramine 50 mg IV with methylprednisolone 100 mg IV (or equivalent), as needed. Patient should be monitored until the investigator is comfortable that the symptoms will not recur; nivolumab or ipilimumab will be permanently discontinued. Investigators should follow their institutional guidelines for the treatment of anaphylaxis. Remain at bedside and monitor patient until recovery from symptoms. In the case of late-occurring hypersensitivity symptoms (e.g. appearance of a localized or generalized pruritus within 1 week after treatment), symptomatic treatment may be given (e.g. oral antihistamine, or corticosteroids).

Please note that late occurring events including isolated fever and fatigue may represent the presentation of systemic inflammation. Please evaluate accordingly.

**7.2 Duration of Therapy**

Patients should continue on trial treatment until RECIST 1.1/iRECIST defined progression or unacceptable toxicity or other treatment discontinuation criterion is met (see below).

An individual patient will not receive any further investigational product if any of the following occur in the patient in question:

- Patient request.

- Lost to follow-up.
- Patient is determined to have met one or more of the exclusion criterion for the trial.
- Participation at trial entry and continuing investigational therapy might constitute a safety risk.
- Pregnancy or intent to become pregnant.
- Initiation of alternative anti-cancer therapy including another investigational agent.

There is no maximum duration of treatment as patients may continue to receive investigational product beyond RECIST 1.1/iRECIST defined progression as long as they are continuing to show clinical benefit. In such cases, patients may continue to receive treatment following objective progression at Investigator's discretion and as agreed with the patient.

### 7.3 Concomitant Therapy

Details of any concomitant medications (prescription, non-prescription, or over-the-counter medications) taken by the patient at study entry and during protocol therapy must be recorded on the appropriate electronic case report forms (eCRFs).

#### 7.3.1 Permitted

- Supportive care for disease-related symptoms may be offered to all patients on the trial.
- Patients are permitted to use topical, ocular, intra-articular, intranasal, and inhalational corticosteroids (with minimal systemic absorption). Physiologic replacement doses of systemic corticosteroids are permitted, even if  $> 10$  mg/day prednisone equivalents. A brief course of corticosteroids for prophylaxis (e.g. contrast dye allergy) or for treatment of non-autoimmune conditions (e.g. delayed-type hypersensitivity reaction caused by contact allergen) is permitted.

#### 7.3.2 Not Permitted

- Immunosuppressive agents (except to treat a drug-related adverse event)
- Systemic corticosteroids  $> 10$  mg daily prednisone equivalent (except as stated in Section 7.1 and 7.3.1 to treat a drug-related adverse event).
- Any concurrent antineoplastic therapy (i.e. chemotherapy, hormonal therapy, immunotherapy, radiation therapy) except for palliative radiation therapy or standard or investigational agents for treatment of cancer.

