4.3.8 Patients with serious illnesses or medical conditions which would not permit the patient to be managed according to the protocol (including corticosteroid administration), or would put the patient at risk. This includes but is not limited to:

- History of significant neurologic or psychiatric disorder which would impair the ability to obtain consent or limit compliance with study requirements.

- Active infection requiring systemic therapy; (including any patient known to have active hepatitis B, hepatitis C or human immunodeficiency virus (HIV) or tuberculosis or any infection requiring systemic therapy).
- Active peptic ulcer disease or gastritis.
- Active pneumonitis.

4.3.9 Patients receiving concurrent treatment with other anti-cancer therapy or other investigational anti-cancer agents.

4.3.10 Patients who have experienced untreated and/or uncontrolled cardiovascular conditions and/or have symptomatic cardiac dysfunction (unstable angina, congestive heart failure, myocardial infarction within the previous year or cardiac ventricular arrhythmias requiring medication, history of 2nd or 3rd degree atrioventricular conduction defects).

4.3.11 Pregnant or lactating women.

4.3.12 Men who are sexually active with women of childbearing potential and women of childbearing potential must agree to use adequate contraception as described in Section 4.2.8.

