#### 8.2.1 Measurable Disease

Measurable tumor lesions (nodal, subcutaneous, lung parenchyma, solid organ metastases) are defined as those that can be accurately measured in at least one dimension (longest diameter to be recorded) as  $\geq 20$  mm with chest x-ray and as  $\geq 10$  mm with CT scan or clinical examination. Bone lesions are considered measurable only if assessed by CT scan and have an identifiable soft tissue component that meets these requirements (soft tissue component  $\geq 10$  mm by CT scan). *Malignant lymph nodes* must be  $\geq 15$  mm in the short axis to be considered measurable; only the short axis will be measured and followed. All tumor measurements must be recorded in millimeters (or decimal fractions of centimeters). Previously irradiated lesions are not considered measurable unless progression has been documented in the lesion.

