8.2.5 Response

All patients will have their BEST RESPONSE from the start of study treatment until the end of treatment classified as outlined below:

**Complete Response (CR):** disappearance of *target* and *non-target* lesions and normalization of tumor markers. Pathological lymph nodes must have short axis measures  $< 10$  mm (Note: continue to record the measurement even if  $< 10$  mm and considered CR). Residual lesions (other than nodes  $< 10$  mm) thought to be non-malignant should be further investigated (by cytology specialized imaging or other techniques as appropriate for individual cases [Seymour 2017]) before CR can be accepted. Confirmation of response is only required in non-randomized studies.

**Partial Response (PR):** at least a 30% decrease in the sum of measures (longest diameter for tumor lesions and short axis measure for nodes) of target lesions, taking as reference the baseline sum of diameters. Non target lesions must be non-PD. Confirmation of response is only required in non-randomized studies.

**Stable Disease (SD):** Neither sufficient shrinkage to qualify for PR nor sufficient increase to qualify for PD taking as reference the smallest sum of diameters on study.

Progressive Disease (PD): at least a 20% increase in the sum of diameters of measured lesions taking as references the smallest sum of diameters recorded on study (including baseline) AND an absolute increase of  $\geq 5$  mm. Appearance of new lesions will also constitute progressive disease (including lesions in previously unassessed areas). In exceptional circumstances, unequivocal progression of non-target disease may be accepted as evidence of disease progression, where the overall tumor burden has increased sufficiently to merit discontinuation of treatment or where the tumor burden appears to have increased by at least 73% in volume. Modest increases in the size of one or more non-target lesions are NOT considered unequivocal progression. If the evidence of PD is equivocal (target or non-target), treatment may continue until the next assessment, but if confirmed, the earlier date must be used.

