## 11.0 CENTRAL REVIEW PROCEDURES

11.1 Central Radiology Review

As part of the trial, copies of x-rays and/or scans may be collected to evaluate cancer response to treatment. There will be no central radiology review for this study.

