### 13.3 Sample Size and Duration of Study

Approximately 100 immunotherapy-naïve patients with *POLE* or *POLD1* mutations identified at study entry via either circulating tumor DNA (cfDNA) central testing or prior local tumor assessment (to be confirmed retrospectively in such patients via central cfDNA testing) will be enrolled to this open-label, randomized, non-comparative trial.

We hypothesize that for this analysis treatment with immunotherapy will show a clinically relevant ORR of > 30% with single agent nivolumab or > 50% with combination nivolumab + ipilimumab in patients with advanced solid tumors with detectable *POLE* or *POLD1* mutations.

A sample size of 50 evaluable patients in each arm will achieve 90% power to show a clinically meaningful ORR. These calculations assume a single agent  $p_0 < 13\%$ ,  $p_1 > 30\%$  and combination therapy  $p_0 < 30\%$ ,  $p_1 > 50\%$ . Both assume a two-sided  $\alpha$  and  $\beta$  of 0.10.

Additional enrollment of up to 20% will be permitted as needed to replace patients found to not demonstrate *POLE* or *POLD1* mutations on central cfDNA.

As additional blood-based assays become available, the study may be amended to include additional cohorts.

Patients will be accrued from approximately four cancer treatment centers in the United States and four cancer treatment centers across Canada over a period of approximately 24 months.

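### Section 7.3.2 contradicts 7.2 on other cancer agents, and no response rule covers a target lesion irradiated on study, so an arm's ORR can be overstated

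*Combined protocol and SAP*

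**What the plan says.** **Concurrent therapy.** Three sections of the protocol bear on this.
- 7.3.2, under its heading of prohibited treatments, bans concurrent antineoplastic therapy "except for palliative radiation therapy or standard or investigational agents for treatment of cancer".
- 7.2 lists, among the events after which a patient gets no further investigational product: "Initiation of alternative anti-cancer therapy including another investigational agent".
- 4.3.9 excludes at entry: "Patients receiving concurrent treatment with other anti-cancer therapy or other investigational anti-cancer agents".

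**Response.**
- 8.2.5 sets the window: "All patients will have their BEST RESPONSE from the start of study treatment until the end of treatment classified as outlined below". A partial response is a fall of at least 30% in the sum of target-lesion measures from baseline, with non-target disease not progressing. It adds: "Confirmation of response is only required in non-randomized studies".
- 8.2.3 asks for a value for every target lesion at each assessment, and 8.6 repeats this for all lesions recorded at baseline.
- On irradiated lesions, 8.2.1 says: "Previously irradiated lesions are not considered measurable unless progression has been documented in the lesion". 8.2.2 makes the matching statement for irradiated areas.
- 11.1 says: "There will be no central radiology review for this study".

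**Analysis.** 13.2 reports ORR per arm with 90% exact confidence intervals. 13.3 states: "A sample size of 50 evaluable patients in each arm will achieve 90% power to show a clinically meaningful ORR". Its assumptions are 13% against 30% for nivolumab and 30% against 50% for the combination.

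**The concern.** There are two separate faults.

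The first is a contradiction. Taken at its word, the exception in 7.3.2 leaves almost nothing of the ban it qualifies and conflicts with 7.2. A site cannot tell from the text whether a patient may take another cancer agent while on study drug.

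The second is a gap in the endpoint. Palliative radiation is exempt on any reading of 7.3.2, and 7.2 does not say whether it counts as alternative anti-cancer therapy. 7.2 also sets no maximum treatment duration, so radiation during the response window is foreseeable. If the irradiated lesion is a target lesion, it must still be measured and its shrinkage enters the response sum. A local effect of radiation can then be credited to study drug.

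At stake is the primary endpoint. The trial is non-comparative and each arm is held against its own fixed null rate, so a similar bias in both arms does not cancel. Response needs no second scan and has no central read, so no later step would remove a misattributed response.

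**Working it through.** **1. The text, side by side**

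| Situation on study | What the protocol provides |
|---|---|
| Another cancer agent is started | 7.3.2 read literally: allowed. 7.2: no further study drug. |
| Palliative radiation is given | 7.3.2: allowed. 7.2: does not say whether it is alternative anti-cancer therapy. |
| A target lesion is irradiated on study | 8.2.3, 8.6: still measured. 8.2.1, 8.2.2: concern measurability of previously irradiated lesions. 8.2.5, 13.2: no rule. |
| A scan after radiation shows a fall of at least 30% in the sum | 8.2.5: partial response if non-target disease is not progressing; Table 1 also requires no new lesion. |

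**2. When can one irradiated lesion produce a partial response?** Let the lesion make up a share *w* of the baseline target sum and shrink by a fraction *s*, the others unchanged. The sum falls by *w* × *s*, and partial response needs *w* × *s* ≥ 0.30.
- Lesion disappears (*s* = 1): *w* ≥ 0.30.
- Lesion halves (*s* = 0.5): *w* ≥ 0.30 / 0.5 = 0.60.
- Only target lesion (*w* = 1; 4.1.4 requires just one measurable lesion): *s* ≥ 0.30.

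The values of *s* are examples. The event is possible but not automatic.

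**3. Reproducing the plan's power.** Inputs from 13.3: n = 50 per arm, two-sided alpha 0.10 (upper tail 0.05), p0/p1 = 0.13/0.30 and 0.30/0.50.

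Normal approximation: power = Φ{[(p1 − p0)√n − 1.645√(p0(1 − p0))] / √(p1(1 − p1))}.
- Nivolumab: (0.17 × 7.071 − 1.645 × 0.336) / 0.458 = 1.42, power 0.922.
- Combination: (0.20 × 7.071 − 1.645 × 0.458) / 0.500 = 1.32, power 0.907.

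The arcsine approximation gives 0.909 and 0.897. The stated 90% is reproduced.

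**4. Cut-offs.** The plan states none. The smallest *r* with P(X ≥ r | 50, p0) ≤ 0.05 is:
- Nivolumab: r = 12, tail 0.024 (r = 11 gives 0.053); exact power 0.861.
- Combination: r = 21, tail 0.048 (r = 20 gives 0.085); exact power 0.899.

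These are also the smallest counts whose 90% exact interval lies above p0: lower limits 14.5% for 12/50 and 30.1% for 21/50, against 12.9% for 11/50 and 28.3% for 20/50. So they fit the reporting in 13.2.

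**5. Effect of *j* false responders.** Suppose *j* of the 50 are counted as responders whatever their true status, and the other 50 − j respond at rate p0. The chance of passing is P(Y ≥ r − j), with Y ~ Binomial(50 − j, p0).

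| j (assumed) | Nivolumab, r = 12 | Combination, r = 21 |
|---|---|---|
| 0 | 2.4% | 4.8% |
| 1 | 4.7% | 7.0% |
| 2 | 8.7% | 10.0% |
| 3 | 15.0% | 14.0% |

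Each true non-responder counted as a responder adds 1/50 = 2 percentage points to the arm's ORR.

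**The case against.** **Other agents.** A reader might infer that any later shrinkage, including shrinkage from another cancer agent, counts as a study-drug response. The documents do not support that. Best response closes at end of treatment, and 7.2 stops study drug when alternative anti-cancer therapy starts. If 7.2 is followed, this route is largely closed. The last words of the 7.3.2 exception stand under a heading of prohibited treatments and may be a drafting slip for a further banned item. This stands: for agents, the fault is mainly a contradiction and is not evidence of a biased ORR.

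**Existing text on irradiated lesions.** 8.2.1 and 8.2.2 are not expressly confined to baseline, and a careful investigator might use them to drop a lesion irradiated on study. That is fair, but they address whether a lesion is measurable and do not tell the site to stop counting one already in the target sum, while 8.2.3 asks for its value each time.

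**Difficulty of reaching a partial response.** The fall is judged on the whole target sum, with no new lesion and no progression elsewhere. Radiation to a non-target bone site cannot by itself create a response. Section 10.1 also makes a need for increased palliative radiation incompatible with clinical stability in patients with unconfirmed progression. All this lowers the likely frequency, but does not cover a patient with stable disease and one dominant target lesion.

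**Size.** The number of false responders is assumed and the cut-offs are derived. If every false responder is instead taken from the true non-responders, so that P(X ≥ r − j | 50, p0) applies, the figures are 5.3%, 10.7% and 19.5% (nivolumab) and 8.5%, 14.1% and 21.8% (combination). The smaller set is used here because the documents give no ground for assuming that only true non-responders are affected.

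**Conclusion.** The point holds in two parts. First, 7.3.2 as worded contradicts 7.2 and fits badly with 4.3.9, and the passages must be reconciled. Second, the response rules let a target lesion irradiated on study contribute to a partial response that needs no confirmation and has no central read. Following those rules can overstate an arm's ORR.

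The size cannot be derived from the documents, because they give no rate of on-study radiation to target lesions. Under the assumptions above, one false responder leaves nivolumab within the nominal 5% upper tail (4.7%) and takes the combination past it (7.0%). Two take both arms past it (8.7% and 10.0%). These figures show how sensitive a trial of 50 per arm is; they do not forecast its error rate. The change should be made, since it touches the primary endpoint at little cost.

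**What to change.** 1. Reconcile 7.3.2 with 7.2 and 4.3.9, so that one reading of concurrent cancer therapy remains, and say whether palliative radiation falls under the stopping rule in 7.2. The choice of clinical rule belongs to the sponsor.
2. In 8.2.5 and 13.2, state that a target lesion irradiated on study is not evaluable for response from the date of radiation. A response documented earlier is unaffected. Table 1 already has a category for target lesions not all evaluated.
3. In the same places, state that a response first documented after other non-protocol anticancer therapy does not count towards ORR.
4. Record the site and date of on-study radiation on the CRF. Section 7.3 requires only concomitant medications to be recorded.

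Items 2 to 4 concern endpoint handling and data capture and change no patient's care. The cost is a few sentences and perhaps a small CRF addition. The downside is that a few patients may become non-evaluable or non-responders, including some whose shrinkage was in truth due to study drug.

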## 8.0 CRITERIA FOR MEASUREMENT OF STUDY ENDPOINTS

### 8.1 Definitions

#### 8.1.1 Evaluable for Adverse Events

All patients will be evaluable for adverse event evaluation from the time of their first treatment.

#### 8.1.2 Evaluable for Response

All patients who have received at least one cycle of therapy and have their disease re-evaluated will be considered evaluable for response (exceptions will be those who exhibit objective disease progression prior to the end of cycle 1 who will also be considered evaluable). Patients on therapy for at least this period and who meet the other listed criteria will have their response classified according to the definitions set out below [Seymour 2017].

Response and progression will be evaluated in this study using the revised international criteria (1.1) proposed by the RECIST (Response Evaluation Criteria in Solid Tumors) committee as well as the modified iRECIST guidelines [Seymour 2017]. Investigators should note the different requirements for confirmatory scans as well as follow up for the two criteria.

